6.3. Measures to Minimize Bias: Randomization and Blinding

Participants who meet the screening eligibility criteria will be randomised to a treatment group through the Interactive Web Response System (IWRS). Before the study is initiated, the log in information and directions for the IWRS will be provided to the site.

Once assigned, a randomisation number must not be reassigned to another participant in the study. This will be a double blind study with both the investigator and participant blinded to study treatment. Site personnel will remain blinded. There will, however, be an unblinded site pharmacy personnel to prepare the study intervention; but they will not have contact with study participants

The following will apply:

- The IWRS will be programmed with blind-breaking instructions. In case of an emergency, the investigator has the sole responsibility for determining if unblinding of a participants' intervention assignment is warranted. Participant safety must always be the first consideration in making such a determination.
- If the investigator decides that unblinding is warranted, the investigator should make every effort to contact GSK prior to unblinding a participant's intervention assignment unless this could delay emergency intervention of the participant. If a participant's intervention assignment is unblinded, GSK must be notified within 24 hours after breaking the blind.
- The date and reason that the blind was broken must be recorded in the source documentation and case report form, as applicable.
- GSK's Safety and Medical Governance (SMG) staff may unblind the intervention assignment for any participant with an SAE. If the SAE requires that an expedited regulatory report be sent to one or more regulatory agencies, a copy of the report, identifying the participant's intervention assignment, may be sent to investigators in accordance with local regulations and/or GSK policy.
- Sites will be required to make every effort to ensure that the results of study laboratory tests are not proactively communicated to participants during the study unless essential for clinical care.

GSK3858279 PK and Free and Total CCL17 results that may unblind the study will not be reported to investigative sites or blinded personnel until the study has been unblinded.

A participant will be withdrawn if the participant's intervention code is unblinded by the investigator or treating physician. The primary reason for discontinuation (the event or condition which led to the unblinding) will be recorded in the CRF. The participant will be followed up for safety monitoring if treatment was received

GSK's Safety Evaluation and Risk Management (SERM) staff may unblind the intervention assignment for any participant with an SAE. If the SAE requires that an expedited regulatory report be sent to one or more regulatory agencies, a copy of the report, identifying the participant's intervention assignment, may be sent to investigators in accordance with local regulations and/or GSK policy.

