6.5. Continued Access to Study Intervention after the End of the Study

This is a single dose study in healthy participants. No study intervention will be provided following the end of the study.

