7. DISCONTINUATION OF STUDY INTERVENTION AND PARTICIPANT DISCONTINUATION/WITHDRAWAL

7.1. Discontinuation of Study Intervention

This is a single dose study. In rare instances a participant may not be able to receive the 4 injections and it may be necessary for the participant to permanently discontinue study intervention. If study intervention is discontinued, the participant will remain in the study for the planned duration.

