7.3. Participant Discontinuation/Withdrawal from the Study

- A participant may withdraw from the study at any time at his/her own request or may be withdrawn at any time at the discretion of the investigator for safety, behavioural, or compliance reasons.
- At the time of discontinuing from the study, if possible, an early discontinuation visit should be conducted, as shown in the SoA. See SoA for data to be collected at the time of study discontinuation and follow-up and for any further evaluations that need to be completed.
- The participant will be permanently discontinued from the study at that time.
- If the participant withdraws consent for disclosure of future information, the sponsor may retain and continue to use any data collected before such a withdrawal of consent.
- If a participant withdraws from the study, he/she may request destruction of any samples taken and not tested, and the investigator must document this in the site study records.

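### Withdrawing a dosed participant after a physician code break ends scheduled PK, CCL17 and ADA sampling in a single-dose study, with little protection against bias in return

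*Protocol*

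**What the plan says.** Protocol 6.3, among the measures against bias, states: "A participant will be withdrawn if the participant's intervention code is unblinded by the investigator or treating physician". It then adds: "The participant will be followed up for safety monitoring if treatment was received". No other assessment is named as continuing.

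The same section sets the trigger: "In case of an emergency, the investigator has the sole responsibility for determining if unblinding of a participants' intervention assignment is warranted". Separately, sponsor safety staff "may unblind the intervention assignment for any participant with an SAE", and an expedited report that identifies the arm may then reach investigators. No withdrawal is attached to that second route.

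Three other sections bear on what withdrawal means here.
- Protocol 6.5: "This is a single dose study in healthy participants. No study intervention will be provided following the end of the study".
- Protocol 7.3, for a participant leaving the study: if possible, "an early discontinuation visit should be conducted, as shown in the SoA", and then "The participant will be permanently discontinued from the study at that time".
- Protocol 7.1, for a participant who cannot receive all four injections: "If study intervention is discontinued, the participant will remain in the study for the planned duration".

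PK is a co-primary objective with safety (Protocol 9.1, SAP 2). AUC(0-56) and Cmax are the two parameters that are modelled (SAP 4.2.1.2). An evaluable participant needs all PK data to Day 57 (Protocol 9.3). The synopsis gives withdrawal before Day 57 as its example of a case for replacement. No sensitivity analyses are planned (SAP 4.2.3, 4.3.3).

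**The concern.** In a multiple-dose trial, withdrawal after a code break at least ends exposure. Here a dosed participant has nothing left to stop, so the only effect of the rule is on data collection.

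The rule appears under bias control, yet PK, free and total CCL17 and ADA are laboratory measurements. That knowing the arm has little route to alter them is an inference, since the documents do not discuss it, but it is a safe one. The part of the data that unblinding can influence is AE reporting and causality, and that is the part 6.3 keeps.

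The loss is also not random. The investigator's code break is tied to an emergency. Protocol 2.3.1 links hypersensitivity to anti-drug antibodies and lists immunogenicity sampling at intervals as mitigation. So the rule can cut short the exposure and antibody record in a participant for whom that record is of most interest. A replacement restores the count but not that participant's data.

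**Working it through.** **1. What the rules do to a dosed participant.**

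| Situation | Source | Stays in study? | Scheduled PK, CCL17 and ADA sampling |
|---|---|---|---|
| Code broken by investigator or treating physician | Protocol 6.3, 7.3 | No; safety follow-up only | Ends, apart from an early-withdrawal visit if possible |
| Code broken by sponsor safety staff after an SAE | Protocol 6.3 | No withdrawal stated | Continues |
| Not all four injections given | Protocol 7.1 | Yes, planned duration | Continues |

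Protocol 8.2 (safety), 8.4 (PK), 8.5 (target engagement) and 8.8 (immunogenicity) are separate sections. Safety monitoring, read plainly, is therefore 8.2. As far as the schedule can be read, the early-withdrawal column includes PK, target engagement and immunogenicity samples.

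**2. What is lost and what is kept.** One reportable value puts a participant in the PK set (if on active) or the TE set (SAP 3), so earlier samples stay. Cmax and tmax survive if the break comes after the peak. AUC(0-t) can be derived from a partial profile. A non-compartmental AUC(0-56) needs sampling to Day 57. CCL17 values at Days 7, 14, 28 and 56 post-dose are lost where they fall after the break. A break after Day 57 leaves the co-primary PK untouched.

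**3. The plan's own allowance.** Seven active are randomised for 6 evaluable: 6/(1 − 1/7) = 7, an allowance of one loss in 7 (14.3%) per cohort. Three placebo for 2 also allows one loss. The simulation behind the 6 is redacted and cannot be reproduced.

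**4. How often.** The documents give no code-break rate, so p per participant is assumed. With 3 × 7 = 21 active:
- At least one active participant affected = 1 − (1 − p)^21: 19% at p = 1%, 35% at 2%, 66% at 5%.
- At least one cohort below 6 active from this cause alone, before replacement = 1 − (1 − q)^3, where q is the chance of two or more losses among 7: 0.6%, 2.3% and 12.7%.

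**5. Precision.** The 90% CI around a ratio of 1.00 is exp(± t(0.95, df) × s × √(1/n1 + 1/n2)), with s = √ln(1 + CV²) and df = N − 4 (ethnicity plus log body weight). It ignores the variance cost of weight imbalance, and the CV is assumed.

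| CV | 7 v 7 (df 17) | 6 v 7 (df 16) |
|---|---|---|
| 20% | 0.83–1.20 | 0.83–1.21 |
| 30% | 0.76–1.31 | 0.75–1.33 |
| 40% | 0.70–1.43 | 0.69–1.45 |

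Losing one participant hardly widens the interval.

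**6. Shift in the estimate.** Let the other six have geometric mean G and the lost participant f × G. The seven together have geometric mean G × f^(1/7). After the loss it is G, so the factor is f^(-1/7):
- f = 0.7: 1.052
- f = 0.5: 1.104
- f = 0.25: 1.219

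In the SAP's ethnicity-only model, the ratio to Caucasians moves by the same factor if the loss is in an Asian cohort, and by its reciprocal (1/1.104 = 0.906 at f = 0.5) if it is in the Caucasian cohort. The values and direction of f are assumed; f above 1 shifts the mean the other way. The calculation also assumes that AUC(0-56) is wholly lost for that participant.

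**The case against.** The other side has real points, and most of them limit the size of the problem.

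- **A reader might infer that the PK, CCL17 and ADA data are discarded.** They are not. Only sampling after withdrawal is lost, parameters are derived as data permit, and SAP 4.2.1 allows model-based methods, which might recover AUC(0-56) from a truncated profile. This stands.
- **A reader might infer that the rule falls on exactly the participants with serious reactions.** It does not. The trigger is a code break by the investigator or treating physician. An SAE without one, or one unblinded by the sponsor, triggers no withdrawal. This stands.
- **A reader might call 6.3 and 7.1 contradictory.** The triggers differ, and in most cases both can be followed. They are inconsistent in approach and collide only if injections are cut short and the code is also broken.
- **Event-related samples can be obtained by other means.** Protocol 8 allows unscheduled samples for safety, 10.3.3 obliges the investigator to obtain further measurements where indicated or requested, and 10.6 asks for a PK sample after a liver event. Safety monitoring could also be read to include ADA. This stands in part: such samples may help to explain the event, but they do not restore the scheduled profile to Day 57.
- **The illustration is assumed.** No document links a code break to low exposure. The factor f^(-1/7) also requires f relative to the other six. Measured against a mean that includes the lost participant it would be f^(-1/6), or 1.06, 1.12 and 1.26. This stands, and the figures are offered only as scale.

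**Conclusion.** The point holds in limited form. Protocol 6.3 states a rule, not merely an omission. After a physician code break, a dosed participant leaves the scheduled PK, CCL17 and ADA sampling, for an event-related reason, while no treatment is stopped and the assay endpoints gain little protection. The uneven treatment of sponsor unblinding weakens the bias rationale further, because an investigator may learn the arm by that route and the participant stays.

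The consequence is small in expectation. Code breaks should be infrequent in healthy volunteers given one dose (an assumption), precision barely changes, and a 5% or 10% shift in one cohort's geometric mean lies inside the 90% interval at an assumed CV of 20% or more. The study tests no hypothesis. What cannot be recovered is one participant's later exposure, target engagement and antibody data, in a cohort of about seven active. This is a cheap improvement rather than a flaw that threatens the study's conclusions.

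**What to change.** Amend Protocol 6.3 so that a dosed participant whose code is broken is not withdrawn from the study for that reason alone. With consent, and subject to the investigator's existing discretion in 7.3 to withdraw a participant, that participant continues the scheduled safety, PK, target-engagement and immunogenicity assessments. Participants unblinded before any injection need not be affected.

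Keep the existing requirement to record the date and reason for the code break, add a flag that marks later AE and causality assessments as unblinded, and align 6.3 with 7.1 and 7.3.

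The cost is protocol wording and one data flag; the visits and samples are already in the schedule. The downside is that later AE and causality assessments for that participant are made unblinded. The flag identifies them but does not remove the effect. The safety follow-up that 6.3 already requires carries the same limitation.

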6.4. Study Intervention Compliance

- When participants are dosed at the site, they will receive study intervention directly from the investigator or designee, under medical supervision. The date and time of each dose administered in the clinic will be recorded in the source documents. The dose of study intervention and study participant identification will be confirmed at the time of dosing by a member of the study site staff other than the person administering the study intervention.

6.5. Continued Access to Study Intervention after the End of the Study

This is a single dose study in healthy participants. No study intervention will be provided following the end of the study.

6.6. Treatment of Overdose

For this study, any dose of GSK3858279 greater than the scheduled dose will be considered an overdose.

In the event of an overdose, the investigator should:

- Contact the Medical Monitor immediately.
- Closely monitor the participant for AE/SAE and laboratory abnormalities until the study intervention can no longer be detected systemically (at least 5 half-lives but not less than 90 days). Document the quantity of the excess dose as well as the duration of the overdosing in the CRF.

Decisions regarding dose interruptions or modifications will be made by the investigator in consultation with the Medical Monitor based on the clinical evaluation of the participant.

GSK does not recommend specific treatment for an overdose.

6.7. Concomitant Therapy

Any medication or vaccine (including over-the-counter or prescription medicines, recreational drugs, vitamins, and/or herbal supplements) or other specific categories of interest that the participant is receiving at the time of enrolment or receives during the study must be recorded along with:

- reason for use
- dates of administration including start and end dates
- dosage information including dose and frequency

The medical monitor should be contacted if there are any questions regarding concomitant or prior therapy.

Participants must abstain from taking prescription or non-prescription drugs (including vitamins, recreational drugs, and dietary or herbal supplements) within 7 days (or 14 days if the drug is a potential enzyme inducer) or 5 half-lives (whichever is longer) before the start of study intervention until completion of the follow-up visit, unless, in the opinion of the investigator and sponsor, the medication will not interfere with the study.

Paracetamol/Acetaminophen, at doses of \leq 3 grams/day, is permitted for use any time during the study. Other concomitant medications may be considered on a case-by-case basis by the investigator in consultation with the medical monitor if required.

7. DISCONTINUATION OF STUDY INTERVENTION AND PARTICIPANT DISCONTINUATION/WITHDRAWAL

7.1. Discontinuation of Study Intervention

This is a single dose study. In rare instances a participant may not be able to receive the 4 injections and it may be necessary for the participant to permanently discontinue study intervention. If study intervention is discontinued, the participant will remain in the study for the planned duration.

7.2. Study Stopping Criteria

If any of the following occur, the study will be temporarily halted:

- Any participant experiences a SAE that can be reasonably attributed to GSK3858279.
- Two or more participants experience the same significant clinical or significant laboratory abnormality that may plausibly relate to GSK3858279 (according to the clinical judgement of the investigator)
- Two participants present with unexplained and clinically significant muco-cutaneous bleeding (according to the clinical judgement of the investigator and medical monitor) that is considered causally related to GSK 3858279

Recruitment may be resumed after appropriate review of safety findings by the Principal Investigators, Medical Monitor and SRT, and following approval to restart the study from the regulatory agencies and ethics committees

[figure not shown]
7.2.1. Liver Chemistry Stopping Criteria

Liver chemistry stopping, and increased monitoring criteria have been designed to assure participant safety and evaluate liver event etiology See Section [10.6](#).

Discontinuation of study intervention for abnormal liver tests is required when:

- a participant meets one of the conditions outlined in the algorithm or
- in the presence of abnormal liver chemistry not meeting protocol-specified stopping rules, if the investigator believes that it is in the best interest of the participant.

Phase 1 Liver Chemistry Stopping Criteria – Liver Stopping Event Algorithm

7.2.2. QTc Stopping Criteria

A subject that meets either bulleted criterion based on the average of triplicate ECG readings will be withdrawn from study intervention.

- QTcF > 500 msec,
- Increase from baseline: QTcF > 60 msec
- In this study as QTcF is used for study eligibility, thus QTcF must be used for discontinuation decisions.
- QTcF has been chosen for a participant's eligibility, the *same formula* must continue to be used for that participant *for all QTc data being collected for data analysis*. Safety ECGs and other non-protocol specified ECGs are an exception.
- If an ECG demonstrates a prolonged QTc, obtain 2 more ECGs over a brief period (see Section), and then use the averaged QTc values of the 3 ECGs to determine whether the subject should be discontinued from the study
- If a clinically significant finding is identified (including, but not limited to changes from baseline in QT interval corrected using Bazett's formula [QTcB] or Fridericia's formula [QTcF]) after enrolment, the investigator or qualified designee will determine if the participant can continue in the study and if any change in participant management is needed. This review of the ECG printed at the time of collection must be documented. Any new clinically relevant finding should be reported as an AE.

7.2.3. SARS-CoV-2 related stopping criteria

N/A

7.3. Participant Discontinuation/Withdrawal from the Study

- A participant may withdraw from the study at any time at his/her own request or may be withdrawn at any time at the discretion of the investigator for safety, behavioural, or compliance reasons.
- At the time of discontinuing from the study, if possible, an early discontinuation visit should be conducted, as shown in the SoA. See SoA for data to be collected at the time of study discontinuation and follow-up and for any further evaluations that need to be completed.
- The participant will be permanently discontinued from the study at that time.
- If the participant withdraws consent for disclosure of future information, the sponsor may retain and continue to use any data collected before such a withdrawal of consent.
- If a participant withdraws from the study, he/she may request destruction of any samples taken and not tested, and the investigator must document this in the site study records.

7.4. Lost to Follow Up

A participant will be considered lost to follow-up if he/she repeatedly fails to return for scheduled visits and is unable to be contacted by the study site.

The following actions must be taken if a participant fails to return to the clinic for a required study visit:

- The site must attempt to contact the participant and reschedule the missed visit as soon as possible, counsel the participant on the importance of maintaining the assigned visit schedule and ascertain whether the participant wishes to and/or should continue in the study.
- Before a participant is deemed lost to follow-up, the investigator or designee must make every effort to regain contact with the participant (where possible, 3 telephone calls and, if necessary, a certified letter to the participant's last known mailing address or local equivalent methods). These contact attempts should be documented in the participant's medical record.
- Should the participant continue to be unreachable, he/she will be considered to have withdrawn from the study.

8. STUDY ASSESSMENTS AND PROCEDURES

- Study procedures and their timing are summarized in the SoA, see Section 1.3
- Protocol waivers or exemptions are not allowed
- Immediate safety concerns should be discussed with the sponsor immediately upon occurrence or awareness to determine if the participant should continue or discontinue study intervention.
- Adherence to the study design requirements, including those specified in the SoA, is essential and required for study conduct.
- All screening evaluations must be completed and reviewed to confirm that potential participants meet all eligibility criteria. The investigator will maintain a screening log to record details of all participants screened and to confirm eligibility or record reasons for screening failure, as applicable.
- Procedures conducted as part of the participant's routine clinical management (e.g., blood count) and obtained before signing of ICF may be utilized for screening or baseline purposes provided the procedure met the protocol-specified criteria and was performed within the timeframe defined in the SoA.
- Safety/laboratory/analyte results that could unblind the study will not be reported to investigative sites or other blinded personnel until the study has been unblinded.
- Repeat or unscheduled samples may be taken for safety reasons or for technical issues with the samples.

8.1. Efficacy and/or Immunogenicity Assessments

Efficacy assessments are not applicable to this study.

Planned timepoints for all immunogenicity assessments are provided in the SoA.

8.2. Safety Assessments

Planned timepoints for all safety assessments are provided in the SoA.

8.2.1. Physical Examinations

- A complete physical examination will include, at a minimum, assessments of the skin, cardiovascular, respiratory, gastrointestinal and neurological systems. Height (at screening only) and weight will also be measured and recorded.
- A brief physical examination will include, at a minimum, assessments of the skin, lungs, cardiovascular system, and abdomen (liver and spleen).
- Investigators should pay special attention to clinical signs related to previous serious illnesses.

